#### **6.5.2 Chronic effects**

To examine for possible chronic effects, changes from baseline (the pre-dosing value on Day 1) to the pre-dosing value on later dosing days and to Day 92, 169, 365 and 456 will be determined. Summaries will be presented in a similar manner to that described for the acute effects.

### **6.6 Interim safety analyses**

Safety data will be reviewed on an ongoing basis by the Sponsor and the Medical Monitor. Safety data will also be reviewed on an ongoing basis by the independent DSMB. The DSMB will be assembled to review safety, tolerability and efficacy data collected on ISIS 396443 during this study and to review the results of the predetermined interim efficacy analysis (Section 5.1). Based on its ongoing assessment of the safety and tolerability of ISIS 396443, the DSMB will provide recommendations to the Sponsor for modifying, stopping or continuing the study as planned.

Details on the safety assessments, frequency of review, meeting schedules and controlled access to unblinded data at the interim safety analyses are outlined in the DSMB Charter.

## **7 Pharmacokinetic data**

CSF and Plasma samples will be collected at protocol designated times for ISIS 396443 pharmacokinetic assessments from both treatment groups in the Pharmacokinetic Population. The Pharmacokinetic Population includes all subjects who are randomized and for which there is at least one evaluable post-dose/post-sham procedure pharmacokinetic sample.

### **7.1 CSF Concentration Data**

CSF concentrations of ISIS 396443, along with the scheduled (nominal) and actual sampling times (i.e., time from IT dosing) will be listed (when applicable) for each patient, and day. Differences between scheduled and actual sampling days will also be listed for all patients. Percent differences between actual administered dose and nominal dose will also be listed.

CSF concentrations below the lower limit of quantification (LLOQ) will be indicated by “BLQ”. For the purpose of calculating typical descriptive statistics (n, mean, SD, %CV, geometric mean, geometric %CV, median, minimum, and maximum) for CSF concentrations, all BLQ values will be set to zero. Mean CSF concentrations that are BLQ will be presented

as BLQ, and the SD and %CV will be reported as not applicable. Summary statistics of the ISIS 396443 CSF concentrations will be tabulated by day. At the discretion of the pharmacokineticist and/or biostatistician, samples may be excluded from descriptive statistics if there are large deviations between scheduled and actual sampling days or times, or large deviations between actual dose and nominal dose.

Due to the limited CSF samples collected no CSF pharmacokinetic parameters will be calculated.

## **7.2 Plasma Pharmacokinetics**

### **7.2.1 Plasma Concentration Data**

Plasma concentrations of ISIS 396443, along with the scheduled (nominal) and actual sampling times (i.e., time from IT dosing) will be listed (when applicable) for each patient, treatment group, and day. Percentage differences between scheduled and actual sampling times will also be listed for all patients. Percentage differences between actual administered dose and nominal dose will also be listed.

Plasma concentrations below the lower limit of quantification (LLOQ) will be indicated by “BLQ”. For the purpose of calculating typical descriptive statistics (n, mean, SD, %CV, geometric mean, geometric %CV, median, minimum, and maximum) for plasma concentrations, all BLQ values will be set to zero. Mean plasma concentrations that are BLQ will be presented as BLQ, and the SD and %CV will be reported as not applicable. Summary statistics of the ISIS 396443 plasma concentrations will be tabulated by day and scheduled time point. At the discretion of the pharmacokineticist and/or biostatistician, samples may be excluded from descriptive statistics if there are large deviations between scheduled and actual sampling times, or large deviations between actual dose and nominal dose.

ISIS 396443 plasma concentration versus time (actual) profiles from Day 1 to Day 29, for each patient, as well as the mean ( $\pm$ SD) plasma concentration versus time (scheduled) profiles for the applicable treatment group, will be presented graphically on linear and semilogarithmic scales. ISIS 396443 plasma concentration versus time (actual) profiles from Day 29 to Day 456, for each patient, as well as the mean ( $\pm$ SD) plasma concentration versus time (scheduled) profiles for the applicable treatment group, will be presented graphically on linear and semilogarithmic scales. Additionally, ISIS 396443 plasma concentration versus time (actual) profiles (Day 1) from 0 to 8 hours for all patients, as well as the mean ( $\pm$ SD) plasma concentration versus time (scheduled) profiles (0 to 8 hours) for the applicable treatment group will be presented graphically on linear and semilogarithmic scales.

Additional plasma concentration versus time (actual) profiles, for all patients and for individual patients may also be generated, including but not necessarily limited to Day 1, 0 to 24 hours; Day 85, 0 to 4 hours; and comparisons between Day 1 and Day 85, 0 to 8 hours. Samples may be excluded from the mean plots if there are large deviations between scheduled and actual sampling times, or large deviations between actual dose and nominal dose.

### **7.2.2 Plasma Pharmacokinetic Parameters**

Non-compartmental pharmacokinetic analysis of ISIS 396443 will be carried out on each individual subject data set using Phoenix WinNonlin version 6.0 or higher (Pharsight Corporation, Mountain View, CA). Plasma pharmacokinetic parameters in each patient (when applicable) will be determined. For calculation of PK parameters, all BLQ values will

be set to zero. The following plasma PK parameters will be calculated (when applicable) and based on actual sampling times:

- $C_{\max}$ : the maximum observed drug concentration in plasma, and
- $T_{\max}$ : the time at which  $C_{\max}$  occurs.

The following PK parameters may be calculated using actual sampling times where appropriate data exists at the discretion of the pharmacokinetic scientist:

- $AUC_{0-24h}$ : areas under the plasma concentration-time curve from zero time (pre-dose) to 24 hours after the IT administration will be calculated using the linear trapezoidal rule,
- $AUC_{0-8h}$ : areas under the plasma concentration-time curve from zero time (pre-dose) to 8 hours after the IT administration will be calculated using the linear trapezoidal rule, and

Plasma pharmacokinetic parameters (if applicable) will be summarized using descriptive statistics (n, mean, SD, %CV, geometric mean, geometric %CV, median, minimum, and maximum) by treatment group, and day.

Additional plasma pharmacokinetic parameters may be calculated (if applicable) at the discretion of the pharmacokineticist.

Exposure-response relationships between selected pharmacodynamic (included but not limited to change in HFMSE) and pharmacokinetic measures (including but not limited to CSF concentrations, plasma  $AUC_{0-8hr}$ ,  $C_{\max}$ , and plasma trough concentrations) may also be explored (including with and without stratification by antibody status), where appropriate.

## 8 Immunogenicity data

Immunogenicity (IM) testing (anti-ISIS 396443 antibody positivity), using designated plasma samples collected from each study subject, is planned to be conducted and reported.

Immunogenicity plasma samples are to be collected pre-dosing on Days 1, 29, 85, and 274, and on Day 169 and 456. Plasma samples collected at other time points for ISIS 396443 concentration determinations may also be evaluated for IM testing if of further interest and deemed warranted by the pharmacokinetic scientist. An individual sample result will be designated 'antibody positive' based on both positive screening and confirmation assay results (i.e., confirmed positive result), and otherwise will be deemed 'antibody negative'. A study subject will be given 'antibody positive' status if they have at least one confirmed positive sample result at any time during the treatment or post-treatment evaluation periods. A study subject will be given 'antibody negative' status if all evaluated IM sample results are antibody negative and they have at least one evaluable IM result from Day 85 or later during the treatment and post-treatment evaluation periods. Otherwise, a study subject will be given 'antibody inconclusive' status.

The IM incidence and IM incidence rate at each evaluated study time point, and for the overall treatment and post-treatment evaluation period, will be determined and appropriately

summarized, by treatment, as the number of and percentage of evaluated subjects with antibody negative, antibody positive, and antibody inconclusive status. In addition, in antibody positive study subjects, antibody titers of any antibody positive samples will be reported (listed) and also appropriately summarized across subjects and by treatment (e.g., at each evaluated time point, or by observed peak titer values, etc.) at the discretion of the designated study pharmacokineticist and/or statistician.

Antibody positivity in anti-ISIS 396443 antibody-positive subjects will also be designated (when possible) as being either ‘persistent’ or ‘transient’, but only for those subjects in which at least one confirmed antibody positive sample result is followed (>100 days later) by at least one additional IM sample assessment (which can be either a confirmed positive or negative result(s)). Those study patients meeting the above criteria and with at least 2 confirmed positive IM results occurring greater than 100 days apart (~5 immunoglobulin half-lives) will be considered to have a ‘persistent’ antibody response. All other subjects meeting the above criteria will be considered to have a ‘transient’ antibody response. Those remaining anti-ISIS 396443 antibody-positive subjects who do not meet the above criteria will not be classified as either ‘persistent’ or ‘transient’, and thus will be given the designation ‘ND’ (not determinable) for persistent/transient IM status.

When and where warranted, PK (e.g., elevated plasma trough level) and selected safety and efficacy (e.g., HFMSE) results may be further summarized (stratified) by antibody status (antibody negative versus positive subjects) and treatment. In previous clinical trials, only minimal immunogenicity samples have confirmed positive for anti-ISIS 396443 antibodies, therefore, if no, or minimal, patients are designated ‘antibody positive’ stratification by antibody status will not be summarized.

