### **3.4.2 Treatment**

Subjects who meet the eligibility criteria will be admitted to the study center on Study Day 1, undergo pre-dose evaluations, be randomized, and then receive either an LP injection of Study Drug (ISIS 396443) or a sham procedure. Subjects will return to the study center on Days 29, 85, and 274 for follow-up evaluations and subsequent injections/sham procedures. Following the injection/sham procedure on Day 1, subjects will remain at the study center for at least 24 hours post-procedure for safety monitoring. Following the injection/sham procedure on Day 29, 85, and 274 subjects will remain at the study center for at least 6 hours post-procedure for safety monitoring. Safety monitoring visits will occur Study Days 30, 86, 92, 169, and 275 (through the last injection/sham procedure). In addition, the study center will monitor the subject's condition through telephone contact on a monthly basis.

For subjects receiving ISIS 396443, a CSF sample for PK and SMN protein analyses will be taken pre-dose on each injection day in a manner that protects the blind.

If a subject terminates early from the study, they will be encouraged to complete assessments per the Day 456 visit. If a subject is randomized but does not successfully receive the first dose of ISIS 396443/undergo the first sham procedure, they will be replaced.

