## **2 Study design**

This is a Phase 3, multicenter, double-blind, randomized, sham-procedure-controlled study of ISIS 396443 administered intrathecally over 15 months to patients with later-onset SMA. Approximately 117 subjects will be randomized 2:1 to receive a 12 mg dose of ISIS 396443 or undergo a sham procedure as control, respectively. Randomization will be stratified based on the subject's age at screening: <6 years versus  $\geq$ 6 years. A separate randomization list will be used for Japan. If a subject does not successfully receive the first dose of ISIS 396443 or undergo the first sham procedure, they will be replaced.

ISIS 396443 will be administered using a loading regimen (dosing on Study Days 1, 29, and 85) followed by a maintenance dosing 6 months thereafter (Day 274). Subjects randomized to the sham-procedure control group will undergo a sham-procedure on Study Days 1, 29, 85, and 274.

No adjustment of dose is permitted. However, should a concurrent illness prevent the dosing procedure from being performed safely, each scheduled dose may be delayed by up to 4 weeks.

The study will consist of screening, treatment, and post-treatment follow-up-periods. The total duration of participation in the study is approximately 16 months.

Blinded safety data will be reviewed on an ongoing basis by the Sponsor and the Medical Monitor. Unblinded safety data will also be reviewed on an ongoing basis by an independent Data Safety Monitoring Board (DSMB) (Section 6.6). In the protocol it was planned that an interim analysis may be conducted when all subjects will have completed the month 6 assessment and at least 39 will have completed the month 15 assessment. An interim efficacy analysis will be conducted using a targeted cut-off date of 31 August 2016 for the clinical data. At the time of the interim analysis, it is expected that approximately 52 subjects will have attended the Month 15 assessment and all 126 subjects will have had the opportunity to attend the assessment at Month 6 (Section 5.1).

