## 2.2 Treatment

Subjects who meet the eligibility criteria will be admitted to the study center on Day 1, undergo pre-dose evaluations, and then receive either an LP injection of ISIS 396443 or undergo a sham procedure.

Both the sham procedure and ISIS 396443 will be administered by dedicated study personnel who are unblinded to treatment assignment (this will not be any of the key study site personnel such as the Principal Investigator, study coordinator, or outcomes assessors) in a dedicated room and the key study personnel and the parents will not be present during the procedure to ensure blinding of treatment assignment.

ISIS 396443 will be administered as an intrathecal slow bolus (1-3 minute) LP injection. ISIS 396443 will be administered using a ‘spinal anesthesia’ needle and 5 mL syringe. A 22G to 25G spinal anesthesia needle is recommended. The target site for needle insertion is the L3/L4 space, but may be 1 segment above or 1-2 segments below this level, if needed. General anesthesia or sedation may be used for the LP injection procedure depending on institutional guidelines.

Subjects randomized to undergo a sham procedure will have a small needle prick on the lower back at the location where the LP injection would otherwise normally be made in subjects assigned to active treatment. The needle will break the skin but no LP injection or needle insertion into the deeper structures will occur. The needle puncture site will be covered with the same bandage that is used to cover the LP injection normally, thus simulating the appearance of an LP injection. If anesthesia or sedation is used for the LP procedure in ISIS 396443-treated subjects, then in order to maintain the blind, minimal sedation should be used for the sham procedure, following institutional procedures. The study subject will be kept in the procedure room for the same amount of time that subjects administered study drug are kept, thus simulating the time period of a study drug administration procedure.

Study drug and sham kits will be packaged in a blinded fashion. Blinded kits for sham procedure contain artificial CSF (5.0 mL solution per 6 mL vial) that will not be injected but will be used to simulate CSF samples for that subject.

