#### **6.1.7 Adverse events by anti-ISIS 396443 antibody status**

To determine the impact of the formation of anti-ISIS 396443 antibodies on the safety of ISIS 396443, the incidence of adverse events in those ‘persistently’ positive, ‘transiently’ positive, and antibody negative will be presented. The definition of persistence is given in [Section 8](#).

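### SAP 8 does not separate the Day 1 pre-dose antibody sample from post-dose samples, so reactivity present before any drug can be labelled as an antibody response

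*SAP*

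**What the plan says.** SAP 8 sets the sampling: "Immunogenicity plasma samples are to be collected pre-dosing on Days 1, 29, 85, and 274, and on Day 169 and 456". The Day 1 sample is therefore drawn before any drug or sham procedure.

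The same section then classifies each child:

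- **Positive:** "at least one confirmed positive sample result at any time during the treatment or post-treatment evaluation periods".
- **Negative:** "if all evaluated IM sample results are antibody negative", plus at least one evaluable result from Day 85 or later.
- **Inconclusive:** everyone else.
- **Persistent or transient:** assigned only to antibody-positive children who have a confirmed positive followed more than 100 days later by another assessment. Persistent means two confirmed positives more than 100 days apart. The rest of this group are transient. Positive children outside the group are not determinable (ND).

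None of these rules mentions the first dose. On periods, SAP 2 says: "The study will consist of screening, treatment, and post-treatment follow-up-periods". There is no separate baseline period. SAP 2.2, headed Treatment, has eligible children "admitted to the study center on Day 1, undergo pre-dose evaluations, and then receive either an LP injection". Protocol 3.4.2, also headed Treatment, has them "undergo pre-dose evaluations, be randomized, and then receive either an LP injection of Study Drug".

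SAP 6.1.7 tabulates adverse events for persistent, transient and negative children. Its stated aim is: "To determine the impact of the formation of anti-ISIS 396443 antibodies on the safety of ISIS 396443".

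**The concern.** Antibodies present before the first dose were not formed in response to study drug. The plan draws a baseline sample that could show this, but the subject-level rules treat it as one more sample. Elsewhere the SAP does separate the two: adverse events are judged on treatment emergence (SAP 6.1), and post-baseline laboratory results are those taken after the first dose (SAP 6.2).

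The incidence and titer of plasma antibodies form the trial's immunogenicity endpoint (SAP 1.4). At stake are the overall subject-level incidence, the persistent and transient labels, and the adverse event table built on them. Pre-existing reactivity, or assay background, would be read there as a response to the drug. It would also count towards the decision whether there are enough positives to stratify at all.

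**Working it through.** The plan gives no figure to reproduce, so the check applies its rules to its own schedule.

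**Inputs.** Sampling days 1 (pre-dose), 29, 85, 169, 274 and 456, and the classification rules, all from SAP 8. Visit window of ±2 days at Day 85, from SAP 2.4. Dose delay of up to 4 weeks, from SAP 2 and Protocol 8.8. Nominal days are used, with all six samples evaluated.

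**Step 1: a child positive on Day 1 only.** There are two readings of when the treatment period begins.

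- Day 1 pre-dose is inside it, following SAP 2.2 and Protocol 3.4.2. The child is antibody positive. The Day 1 positive is followed more than 100 days later by other samples, and there is no second positive, so the label is transient.
- Treatment starts at the first dose. The child has no positive in the period, but not every evaluated sample is negative, so the label is inconclusive. SAP 6.1.7 has no inconclusive group, so the child drops out of that table.

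On neither reading is the child negative, although all five post-dose samples are.

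**Step 2: gaps from Day 1.**

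- Day 29: 29 − 1 = 28 days
- Day 85: 85 − 1 = 84 days
- Day 169: 169 − 1 = 168 days
- Day 274: 274 − 1 = 273 days
- Day 456: 456 − 1 = 455 days

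A Day 1 positive with a single post-dose positive on Day 169, 274 or 456 exceeds 100 days and is persistent. An on-time Day 85 sample does not reach 100 days (84, or 84 + 2 = 86 at the edge of the window). If the Day 85 dose and its pre-dose sample are 4 weeks late, it does: 84 + 28 = 112.

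**Step 3: all patterns.** Six samples, each positive or negative, give 2^6 = 64 patterns. Each was classified first with Day 1 counted and then with Day 1 left out. Five change label:

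| Days positive | Day 1 counted | Day 1 left out | Reason |
|---|---|---|---|
| 1 | transient | negative | no post-dose positive |
| 1, 169 | persistent | transient | one post-dose positive, later samples exist |
| 1, 274 | persistent | transient | one post-dose positive; Day 456 is 182 days later |
| 1, 85, 169 | persistent | transient | 169 − 85 = 84 days, not over 100 |
| 1, 456 | persistent | ND | nothing follows Day 456 |

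The first row uses the reading with Day 1 inside treatment. On the other reading its change is from inconclusive to negative. The other four rows hold on both readings: each child is antibody positive on a post-dose sample anyway, and the 100-day rule has no period limit.

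**Step 4: what the count leaves out.** Half the patterns, 32, have a positive Day 1. Five change label, so 32 − 5 = 27 keep theirs. Their later positives may still be unchanged pre-existing reactivity, which only a comparison of titers with Day 1 could show. These are counts of possible patterns, not expected numbers of children.

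**The case against.** The strongest reply is that the treatment period starts at the first dose or sham. The SAP often works that way. Its abbreviation list ties the treatment start date to study treatment or sham procedure. SAP 2.2 reports children who were randomized but never dosed as occurring before the start of treatment. SAP 6.1 counts emergence from the first dose. The evidence on the other side is two section headings and a schedule banner that merges treatment with follow-up. This has force against the claim that a Day 1-only child is certainly antibody positive. It does not repair the rules: that child becomes inconclusive rather than negative, and Day 1 can still supply the first of the two persistent positives.

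The second reply is that the result is neither hidden nor uncontrolled. SAP 8 reports incidence at each time point and by treatment, so Day 1 positives can be seen. It lists titers of positive samples in antibody-positive children. A positive needs both a screening and a confirmation result, and sham children provide a concurrent control for background. All of this stands, and it limits the harm. It does not correct the subject-level labels, the overall incidence or the SAP 6.1.7 table.

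The third reply is that little hangs on the labels. The PK, safety and efficacy stratifications by antibody status are optional and are dropped if few or no children are positive. Adverse event tables carry no statistical tests (SAP 6.1.9). This also stands.

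**Conclusion.** The rules in SAP 8 can label a child's pre-dose reactivity as an antibody response, on either reading of when treatment starts. On the scheduled samples, five of 64 result patterns carry a different label because Day 1 is counted. This rests on nominal visit days and a complete set of six samples.

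A reader might infer that the reported incidence will be materially inflated, or that a true antibody effect on safety, PK or HFMSE will be diluted. The documents do not support that. They give no rate of pre-dose positivity and no false-positive rate for the assay, and SAP 8 says only that few samples confirmed positive in earlier trials. What can be said is the weight of one child. With the 84 and 42 children per arm in SAP 5.1, all evaluated, one Day 1-only positive counted as antibody positive moves that arm's overall incidence by 1/84 = 1.2 or 1/42 = 2.4 percentage points.

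A reader might also infer that the Day 1 result is never reported. It is reported by visit; what is missing is its use in subject status. No primary or secondary efficacy test, alpha level or sample size is affected. This is a cheap correction to a named endpoint, not a threat to the trial's main conclusions.

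**What to change.** In SAP 8:

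1. Base positive, negative and inconclusive status, and the persistent/transient rule, on samples taken after the first dose or sham procedure. Include any additional PK samples that are tested. A cut-off at Day 29 would not fit, because SAP 8 allows plasma samples from other time points to be tested.
2. Report Day 1 pre-dose positives separately as pre-existing, by arm.
3. For those children, count a treatment-emergent response only if a later titer exceeds the Day 1 titer by a set threshold. The documents state no threshold, so take it from assay validation and fix it before unblinding.
4. Use this treatment-emergent status in SAP 6.1.7 and in any stratification by antibody status.

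The cost is SAP wording and one extra derived flag. The six scheduled samples, including Day 1, are already planned, and SAP 8 already provides for titers in antibody-positive children. The reported incidence may be slightly lower. A child positive on Days 1 and 456 only would move to ND, for which SAP 6.1.7 has no group.
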